10.8 Windowing Conventions

Actual dates of visits will be used for calculations of time intervals. No visit windowing will be performed for this study. Out-of-window visits will not be reallocated to the nearest timepoint.

10.9 Demographic Characteristics and Medical History

10.9.1 Demographic Characteristics

Demographic parameters, including age, gender, race, body weight, height, and BMI, at Screening, will be summarized for the SAF analysis set.

10.9.2 Medical History

Summary analysis will involve the SAF analysis set.

SMA history parameters, including time (years) from onset of SMA symptoms and SMN gene analysis results will be summarized. Time from onset of SMA symptoms will be calculated as the difference in years from the year of the date of the informed consent and the year of onset of SMA symptoms reported in CRF.

All verbatim terms reported in the Medical History form will be assigned to a Preferred Term (PT) and will be classified by the primary System Organ Class (SOC) according to the Medical Dictionary for Regulatory Activities (MedDRA) thesaurus, version 23.

Previous diseases are those reported in the “Medical History” form of the eCRF with item “*Present at study start?*” flagged as “No”.

Concomitant diseases are those reported in the “Medical History” form of the eCRF with item “*Present at study start?*” flagged as “Yes” or “Unknown”.

The following data will be presented:

- a) A default frequency table showing the number and percentage of patients who exhibited an abnormality by single body system;
- b) A default frequency table showing the number and percentage of patients who exhibited at least one previous disease and the previous diseases by primary SOC and PT;
- c) A default frequency table showing the number and percentage of patients who exhibited at least one concomitant disease and the concomitant diseases by primary SOC and PT;

Medical history will be listed for all enrolled patients.

10.10 Medication and Treatment Analysis

10.10.1 Patient Disposition and Accountability

The number and percentage of patients who are enrolled, in the SAF and ITT_{QOL} analysis set, and who complete Long-term study will be presented. The number and percentage of patients who discontinue dosing prematurely, along with the primary reason that dosing was discontinued prematurely, will be presented.

10.10.2 Duration of Treatment and Compliance

Duration of treatment will be summarized for the SAF analysis set.

The duration of treatment is the (*date of the last study drug dose intake* minus the *date of administration of the first dose of study drug*) +1.

Compliance is 100%*(Number consumed)/(Number prescribed). “Number consumed” is from Study Drug Accountability and “Number prescribed” is number of tablets to have been taken daily duration. Compliance will be summarized for the SAF analysis set.

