10.13 Protocol Deviations

All the protocol deviations will be discussed case by case by the clinical team during the review of the data before the lock of the study database and described in the Data Review Report.

However, the following protocol deviations are anticipated to be considered as major:

- Inclusion and exclusion criteria not respected;
- Missing information on IMP administration that does not allow calculation of IMP exposure/compliance;
- Overall study treatment compliance < 80%;
- Use of prohibited medications during study (see Protocol Section 10.4).

The number and percentage of patients with each type of protocol deviation will be presented.

11 Data Handling

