13.2 Line Listings Specifications

Individual line listings will be provided as defined by the listing shells.

All output will be generated by SAS System and exported into a Microsoft Word document in RTF format. All output will be in landscape orientation. Left and right margins will be 2 cm from the side; the top and bottom margins will be 2.5 cm. Font size will be Courier New 7 pt.

The header containing the sponsor name (Catalyst Pharmaceuticals) and protocol number will appear on the top left corner of each page of the output. The page number, in the format of “Page x of y”, will appear on the top right corner of the output, where y = last page of corresponding output.

The SAS program name, and the date of the creation of the output (run date) will appear on the bottom left corner as follows:

Source: [program name].sas, Run on ddmmmyyyy.

14 Programming Conventions for Outputs

Outputs will be presented according to the standard SPARC’s layout of tables and line listings.

Dates & Times: depending on data available, dates and times will take the form ddmmmyyyy hh:mm (i.e. 01JAN2019 10:20)

Spelling Format: English US.

Listings: all listings will be ordered by the following (unless otherwise indicated in the template):

- Site ID
- Patient number
- Study visit
- Date and hours (where applicable)

In all listings missing data will be reported, according to the variable type, as follows:

- Character variables and dates will be presented as empty fields
- Numerical variables will be presented with a “-“

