Reference Listings: [16.2.7.4.](#)

Programming Note: "Other Body System" is also recorded, but is not included in the above table; it is listed only.

Table 14.1.13. Physical Examination Abnormalities by SOC and PT / SAF

System Organ Class Preferred Term	Statistic	Amifampridine (N=xxx)
No. of patients with at least one abnormality	n (%)	xx (xx.x%)
System Organ Class 1	n (%)	xx (xx.x%)
Preferred Term 1	n (%)	xx (xx.x%)
Preferred Term 2	n (%)	xx (xx.x%)
Preferred Term x	n (%)	xx (xx.x%)
System Organ Class 2	n (%)	xx (xx.x%)
Preferred Term 1	n (%)	xx (xx.x%)
Preferred Term 2	n (%)	xx (xx.x%)
Preferred Term x	n (%)	xx (xx.x%)
System Organ Class x	n (%)	xx (xx.x%)
Preferred Term 1	n (%)	xx (xx.x%)
Preferred Term 2	n (%)	xx (xx.x%)
Preferred Term x	n (%)	xx (xx.x%)

Abnormalities are those reported in the "Physical Examination" form of the eCRF.
Abnormalities were coded using the MedDRA dictionary version 23. Primary System Organ Class and Preferred Term are presented.
Patients are only counted once per SOC and PT.
Patients can have more than one abnormality.
Percentages are calculated on the number of patients (N) in the SAF analysis set.

Source: xxx.sas, Run on ddmmmyyyy

Reference Listings: [16.2.7.4.](#)

Table 14.2.1. Duration of Treatment / SAF

Amifampridine (N=xx)	
Duration of treatment (days)	
n	xx
Mean (SD)	xx.x (xx.xx)
Median	xx.x
Min, Max	xx, xx

Source: xxxx.sas, Run on ddmmmyyyy

Reference Listings: [16.2.5.2.1.](#)

Table 14.2.3. Amifampridine Dosage by Visit / SAF

Visit: Screening	Statistic	Amifampridine (N=xx)
Dose frequency		
3 times per day	n (%)	xx (xx.x)
4 times per day	n (%)	xx (xx.x)
Amifampridine total daily dose (mg)		
	n	xx
	Mean (SD)	xx.x (xx.xx)
	Median	xx.x
	Min, Max	xx, xx

Source: xxx.sas, Run on ddmmmyyyy

Reference Listings: [16.2.5.1.2.](#)

Programming Note: This table will be repeated for all visits (Screening, End of study month 3, End of study month 6, End of study month 9, End of study month 12, End of study month 15, End of study month 21, End of study month 27, EoS, Extra visit).

Table 14.2.4. Treatment Compliance / SAF

	Statistic	Amifampridine (N=xx)
Compliance (%)	n	xx
	Mean (SD)	xx.xx (xx.xxxx)
	Median	xx.xx
	Min, Max	xx.x, xx.x

Compliance is 100%*(Number consumed) / (Number prescribed).

Source: xxx.sas, Run on ddmmmyyyy

Reference Listings: [16.2.5.2.1.](#)

Table 14.3.1. Summary of Treatment Emergent Adverse Events (TEAEs) / SAF

	Statistic	Amifampridine (N=XX)
No. of patients in SAF Population	n	xx

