xxx	xxx	Cardiovascular	Yes	xxxxxxxxxx	xxxxxxxxxx	xxxxxxxxxx	DDMMYYYY	xxx
		Respiratory	Yes	xxxxxxxxxx	xxxxxxxxxx	xxxxxxxxxx	DDMMYYYY	xxx
		Muscle-Skeletal	Yes	xxxxxxxxxx	xxxxxxxxxx	xxxxxxxxxx	DDMMYYYY	xxx
		Ears, nose, eyes and throat	Yes	xxxxxxxxxx	xxxxxxxxxx	xxxxxxxxxx	DDMMYYYY	xxx
		.						
		.						

(1) Involved: No, Yes, Not Examined

(2) Present at study start: No, Yes, UNK

Source: [program name].sas, Run on ddmmmyyyy.

Programming Notes: Continue for Other Body systems ("Hepatobiliary", "Endocrine & Metabolic", "Haemapoietic", "Central Nervous", "Dermatologic", "Genitourinary", "Gastrointestinal", "Psychiatric Diseases", "Allergies" and "Other Body System"). There may be multiple entries for "Other".

Sort by site and patient number.

Listing 16.2.5.1.1. Amifampridine Treatment at Screening

Site	Patient	Screening failure?	Are all inclusion and exclusion criteria satisfied?	Inclusion/Exclusion criteria number(s) not met	First dose (mg)	Timing of first dose (hh:mm)	Second dose (mg)	Timing of second dose (hh:mm)	Third dose (mg)	Timing of third dose (hh:mm)	Fourth dose prescr ibed?	Fourth dose (mg)	Timing of fourth dose (hh:mm)	Total daily dose (mg)	Date of adminis tration of the firs t dose
xxx	xxx	xxx	xxx	xxx	xxx	xx:xx	xxx	xx:xx	xxx	xx:xx	xxx	xxx	xx:xx	xxx	DDMMYY
xxx	xxx	xxx	xxx	xxx	xxx	xx:xx	xxx	xx:xx	xxx	xx:xx	xxx	xxx	xx:xx	xxx	DDMMYY
xxx	xxx	xxx	xxx	xxx	xxx	xx:xx	xxx	xx:xx	xxx	xx:xx	xxx	xxx	xx:xx	xxx	DDMMYY
xxx	xxx	xxx	xxx	xxx	xxx	xx:xx								No	

Source: [program name].sas, Run on ddmmmyyyy.

Programming Note: Sort by site and patient number.

Listing 16.2.5.1.2. Amifampridine Treatment Over the Study

Site	Patient	Timing of first dose		Timing of second dose		Timing of third dose		Fourth dose prescr ibed?		Timing of fourth dose		Total daily dose (mg)
		First dose (mg)	Second dose (hh:mm)	Second dose (mg)	Second dose (hh:mm)	Third dose (mg)	Third dose (hh:mm)	Fourth dose (mg)	Fourth dose (hh:mm)			
xxx	xxx	xxx	xx:xx	xxx	xx:xx	xxx	xx:xx	xxx	xxx	xx:xx	xxx	xxx
xxx	xxx	xxx	xx:xx	xxx	xx:xx	xxx	xx:xx	xxx	xxx	xx:xx	xxx	xxx
xxx	xxx	xxx	xx:xx	xxx	xx:xx	xxx	xx:xx	xxx	xxx	xx:xx	xxx	xxx
xxx	xxx	xxx	xx:xx						No			

Source: [program name].sas, Run on ddmmmyyyy.

Programming Note: Sort by site and patient number.

Listing 16.2.5.2.1 Duration and Compliance over the Study

Site	Patient	Number of tablets dispensed	Number of tablets used	Treatment duration (days)	Compliance (%)
xxx	xxx	xxx	xxx	xxx	xxx.x
xxx	xxx	xxx	xxx	xxx	xxx.x
xxx	xxx	xxx	xxx	xxx	xxx.x

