xxx	xxx	xxx	xxx	xxx	xxx.x
xxx	xxx	xxx	xxx	xxx	xxx.x

Source: [program name].sas, Run on ddmmmyyyy.

Programming Notes: Sort by site and patient number. Number of Tablets Dispensed, Number of Tablets Used, and Treatment Duration are totals from next listing. Compliance is determined from these totals.

Listing 16.2.5.2.2 Study Drug Accountability

Site	Patient	Date of IP dispensing	Visit (1)	Box kit number	No. of tablets dispensed	Start date of period covered with this box	End date of period covered with this box	No. of tablets returned	No. of tablets used	No. of tablets lost	Total tablets used, returned and lost (calculated)	Divided in the following frequency (2)	Total daily dose (mg) (3)
xxx	xxx	DDMMYYYY	xx	xx	xx	DDMMYYYY	DDMMYYYY	xx	xx	xx	xx	xx	xx
		DDMMYYYY	xx	xx	xx	DDMMYYYY	DDMMYYYY	xx	xx	xx	xx	xx	xx
		DDMMYYYY	xx	xx	xx	DDMMYYYY	DDMMYYYY	xx	xx	xx	xx	xx	xx
xxx	xxx	DDMMYYYY	xx	xx	xx	DDMMYYYY	DDMMYYYY	xx	xx	xx	xx	xx	xx
		DDMMYYYY	xx	xx	xx	DDMMYYYY	DDMMYYYY	xx	xx	xx	xx	xx	xx
		DDMMYYYY	xx	xx	xx	DDMMYYYY	DDMMYYYY	xx	xx	xx	xx	xx	xx

(1) Visit: Screening, End of study month 3, End of study month 6, End of study month 9, End of study month 12, End of study month 15, End of study month 21, End of study month 27, EoS, Extra visit

(2) Divided in the following frequency: 3 times per day, 4 times per day

(3) Total Daily Dose (mg): 5, 10, 15, 20, 25, 30, 35, 40, 45, 50, 55, 60, 65, 70, 75, 80

Source: [program name].sas, Run on ddmmmyyyy.

Programming Note: Sort by site and patient number and date of IP dispensing.

Listing 16.2.6.1. Quality of Life (QoL): Type of Questionnaire

Site	Patient	Visit	QoL questionnaire performed?	If No, specify reason	Date of test performed	Time of test performed (hh:mm)	Type of questionnaire (1)
xxx	xxx	Screening	xxx		DDMMYYYY	xx:xx	xxxxxxxxxx
		Month 3	xxx		DDMMYYYY	xx:xx	xxxxxxxxxx
		Month 6	xxx		DDMMYYYY	xx:xx	xxxxxxxxxx
		Month 9	No	xxxxxxxxxx	DDMMYYYY	xx:xx	xxxxxxxxxx
		...	xxx		DDMMYYYY	xx:xx	xxxxxxxxxx
		EOS	xxx		DDMMYYYY	xx:xx	xxxxxxxxxx
xxx	xxx	Screening	xxx		DDMMYYYY	xx:xx	xxxxxxxxxx
		Month 3	xxx		DDMMYYYY	xx:xx	xxxxxxxxxx
		Month 6	xxx		DDMMYYYY	xx:xx	xxxxxxxxxx
		Month 9	xxx		DDMMYYYY	xx:xx	xxxxxxxxxx
		...	xxx		DDMMYYYY	xx:xx	xxxxxxxxxx
		EOS	xxx		DDMMYYYY	xx:xx	xxxxxxxxxx

(1) Type of questionnaire: PEDSQL Parent Report for Young Child (ages 5-7), PEDSQL Parent Report for Child (ages 8-12), PEDSQL teen (ages 13-18), INQOL (ages > 18)

Source: [program name].sas, Run on ddmmmyyyy.

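### The programming note to Listing 16.2.5.2.1 derives treatment duration and compliance from other inputs than SAP 10.10.2, and this listing feeds Tables 14.2.1 and 14.2.4

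*SAP*

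**What the plan says.** SAP 10.10.2 sets duration by dose dates: "The duration of treatment is the (*date of the last study drug dose intake* minus" the date of the first dose, plus one. It sets compliance by "Compliance is 100%*(Number consumed)/(Number prescribed"). Tablets consumed come from drug accountability. The sentence defining tablets prescribed is incomplete: it names a daily tablet count and a duration with nothing joining them, and is presumably meant as their product. The footnote to Table 14.2.4 repeats the ratio: "Compliance is 100%*(Number consumed) / (Number prescribed").

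Tables 14.2.1 (duration) and 14.2.4 (compliance) both cite Listing 16.2.5.2.1 as their source. The programming note to that listing reads: "Number of Tablets Dispensed, Number of Tablets Used, and Treatment Duration are totals from next listing. Compliance is determined from these totals". The listing has a column headed "Number of tablets dispensed" and none for tablets prescribed. The next listing, 16.2.5.2.2, is the accountability record. Its dates are the dispensing date and the start and end of each box period, the latter headed "End date of period covered with this box". The first-dose date is in Listing 16.2.5.1.1 and the last-dose date in Listing 16.2.9.

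SAP 13.2 states: "Individual line listings will be provided as defined by the listing shells". SAP 10.13 includes "Overall study treatment compliance < 80"% among the deviations it expects to class as major.

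**The concern.** A programmer who follows the note will not necessarily get the figures that 10.10.2 defines, and the documents give no rule that ranks SAP text above the shells. For duration, the two texts name different sources outright. For compliance, the note's totals contain neither a prescribed count nor a daily dose, so 10.10.2 cannot be computed from them alone.

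The patient most exposed is one who takes every tablet and then stops partway through a 90- or 180-day supply. Unused tablets go back to the clinic, so tablets dispensed exceed tablets used for a reason unrelated to adherence. If tablets dispensed, or planned supply days, become the denominator, that patient looks non-compliant and may be counted as a major deviator. Duration of exposure may also be overstated, in a study whose primary objective is long-term safety.

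**Working it through.** The plan states no compliance or duration figure to reproduce, so the check compares the possible derivations for one type of patient.

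**Inputs.** Supplies are 90 days, then 180 days from Month 15 (Protocol 13.2), with dispensing from Screening to Month 21 (Schedule of Events). That is five 90-day and two 180-day supplies, cumulatively 90, 180, 270, 360, 450, 630 and 810 days. Tablets are 10 mg. Assumptions: full adherence until stopping, constant dose, supplies of exactly those lengths used in sequence, and leftovers returned.

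**Formulas.** For *t* tablets a day, a stop on day *d*, and *D* days of supply dispensed by then:

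- SAP 10.10.2, read as daily tablets × duration: *td*/(*td*) = 100% on every stop day.
- Note as used/dispensed: *td*/(*tD*) = *d*/*D*.
- Note as used/(daily tablets × box days), with end dates as planned coverage: also *d*/*D*.
- The same, with end dates as actual last use: *td*/(*td*) = 100%.

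The daily dose cancels. At 60 mg/day (6 tablets), a stop on Day 45 gives 540 dispensed and 270 used: 270/(6 × 45) = 100% under 10.10.2, and 270/540 = 50% under the second and third formulas.

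**Results for *d*/*D*.** Day 30: 30/90 = 33%. Day 120: 120/180 = 67%. Day 200: 200/270 = 74%. Day 300: 300/360 = 83%. Day 480: 480/630 = 76%.

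| Supply | *D* (days) | Stop days with *d*/*D* < 80% | Count |
|---|---|---|---|
| 1 | 90 | 1–71 | 71 |
| 2 | 180 | 91–143 | 53 |
| 3 | 270 | 181–215 | 35 |
| 4 | 360 | 271–287 | 17 |
| 5 | 450 | none | 0 |
| 6 | 630 | 451–503 | 53 |
| 7 | 810 | 631–647 | 17 |

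The total is 246 of 810 possible stop days (30%).

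**Duration.** With planned end dates, a Day-120 stop counts as 180 days. Suppose that 1 or 3 of 12 patients stop on Day 120 and the rest complete 810 days (both numbers assumed):

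- One stopper: (11 × 810 + 180)/12 = 757.5 against (11 × 810 + 120)/12 = 752.5, which is +5 days (0.7%).
- Three stoppers: (9 × 810 + 3 × 180)/12 = 652.5 against (9 × 810 + 3 × 120)/12 = 637.5, which is +15 days (2.4%).

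Summing box periods can also depart from 10.10.2 with no early stop. A 14-day gap between two 90-day boxes gives 180 days instead of 90 + 14 + 90 = 194. A 7-day overlap gives 180 instead of 173.

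**The case against.** The strongest reply is that the SAP contains only one compliance formula. The note gives none, and SAP 13.1 ties tables to their shells, so used/dispensed would contradict the footnote printed on Table 14.2.4. Used/dispensed also leaves the note's duration total with no role, whereas duration is needed for used/(daily tablets × days), and Listing 16.2.5.2.2 carries the daily dose. Box end dates stand beside tablets returned, used and lost, which are known only at return, so actual use is a reasonable meaning. On that reading an early stopper with contiguous boxes has the same compliance under both texts.

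Most of this stands. A reader might infer that the shell prescribes used/dispensed; it does not, and that reading is only one way to fill a gap. Nor can the readings be counted as equally likely: the documents do not list them, and they arise only because the note has no formula and the box end date is undefined.

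The reply does not remove the duration conflict, which is in the words themselves. Nor does it supply the prescribed count that the listing lacks. The 100% figure for 10.10.2 also depends on reading its incomplete sentence as a product, so that section needs repair too.

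**Conclusion.** The note is wrong as written, and the consequence is minor. It names a different source for duration from 10.10.2, and inputs for compliance from which the 10.10.2 ratio cannot be formed without adding the daily dose. Depending on how it is programmed, an adherent patient who stops mid-supply is shown at 100% or at a much lower figure, such as 67% for a Day-120 stop. The lower figures rest on the stated assumptions and on used/dispensed or planned box end dates.

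Two stronger conclusions are tempting. A reader might take 246 of 810 as a 30% chance of misclassification. It is a count of days; the documents give no discontinuation rate or timing. A reader might also infer that safety or quality-of-life results are at risk. They are not: the study is descriptive, no analysis set depends on compliance, and stopping for an adverse event is reported separately in Tables 14.1.3 and 14.3.8. SAP 10.13 also has deviations discussed individually before database lock. That review may catch a false flag, although nothing says it would correct Tables 14.2.1 or 14.2.4. With about 12 patients, one false flag moves Table 14.1.5 by 1/12, about 8 percentage points.

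**What to change.** 1. Listing 16.2.5.2.1: replace the programming note with a reference to SAP 10.10.2. Take duration from the first-dose date (Listing 16.2.5.1.1) and the last-dose date (Listing 16.2.9).
2. SAP 10.10.2: replace the incomplete sentence with: *Number prescribed is the sum, over each calendar day from first to last dose counted once, of the prescribed total daily dose on that day / 10 mg.* Counting each day once removes the effect of overlapping box periods.
3. Listing 16.2.5.2.1: add a column for the number of tablets prescribed.
4. SAP 10.13: state that the < 80% item uses this number.

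No special rule for interruption days should be added: no listing shell shows drug stop and restart dates, and 10.10.2 has no such rule now.

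The cost is one replaced note, one column and two SAP sentences. The dose dates, tablets used and daily dose by box period are already in the listings. The shells show no separate date for a dose change between dispensings, so such a change would have to be dated from the study records. SAP section 4 already provides for the document and its shells to be reviewed and revised before the final analyses.

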10.10.3 Concomitant Medications

All prescription and over-the-counter medications and herbal and nutritional supplements taken during the Long-Term study will be recorded on the designated CRF. All prior medications taken within 14 days of initiation of this study are to be recorded on the CRF which is also recorded in the appropriate CRF pages of Study SMA-001 as concomitant medications.

The Investigator may prescribe additional medications during the study if the prescribed medication is not prohibited by the protocol. In the event of an emergency, any needed medications may be prescribed without prior approval, but the medical monitor must be notified of the use of any contraindicated medications immediately thereafter. Any concomitant medications added or discontinued during the study should be recorded on the CRF.

Concomitant medications will be only listed for all enrolled patients.

10.11 Efficacy Analyses

Efficacy will be assessed by changes in QoL over time.

Assessments of efficacy will be performed using the following endpoints:

1. CFB in the INQoL subscales scores:

Symptoms (section 1):

- a) Weakness
- b) Muscle “locking”
- c) Pain
- d) Fatigue
- e) Droopy eyelids
- f) Double vision
- g) Swallowing difficulties

Life domains (section 2):

- a) Activities
- b) Independence

- c) Social relationship
- d) Emotions
- e) Body image

Life domains (section 3):

- a) Perceived treatment effects
- b) Expected treatment effects

Quality of Life

2. CFB in the PEDSQL score (where applicable).

The individual domain scores in INQoL will be calculated using the scoring algorithms outlined in [Appendix 2](#).

Results from INQoL questionnaires and PEDSQL inventory of disease specific symptoms will be summarized with descriptive statistics (n, mean, standard deviation, minimum, median, and maximum) per time point (Months 3, 6, 9, 12, 15, 21 and 27) and CFB, using the Day 0 [in the case where patient completed SMA-001 study, was randomized but not completed SMA-001 study, was not randomized; however based on PI discretion, the patient had benefits and were allowed to enroll in the SMA-002] or the screening visit for the SMA-001 study [in the case where patient had QoL performed at Screening visit of the SMA-001 study, and No QoL was performed on Day 0 or thereafter] response as the baseline level.

The subscales of the INQoL questionnaires will be similarly summarized.

Efficacy analysis will be conducted on ITT_{QOL} analysis set. The efficacy analysis will be descriptive and will be presented on observed data only. Means with standard deviations of INQoL and PEDSQL scores will be also presented.

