**NUMBER OF PATIENTS PLANNED:**

About 12 SMA Type 3 ambulatory patients will be studied.

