### 10.2.2 Exclusion Criteria

Individuals who met any of the exclusion criteria in the original protocol or those listed below are not eligible to participate in the study:

1. Epilepsy and currently on medication.
2. Uncontrolled asthma.
3. Concomitant use with sultopride.
4. Concomitant use with medicinal products with a narrow therapeutic window.
5. Clinically significant abnormalities in 12 lead ECG, in the opinion of the Investigator.

	SMA-002	Page 21
---	---------	---------

6. Breastfeeding or pregnant at Screening or planning to become pregnant at any time during the study.
7. Intolerable amifampridine-related side effects
8. Treatment with an investigational drug (other than amifampridine) or device while participating in this study.
9. Any medical condition that, in the opinion of the Investigator, might interfere with the patient's participation in the study, poses an added risk for the patient, or confound the assessment of the patient.
10. History of drug allergy to any pyridine-containing substances or any amifampridine excipient(s).

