#### **10.3.4 Method of Assigning Patients to Treatment Groups**

All patients will receive open label amifampridine. Details on study drug preparation, dispensing medication will be included in the Pharmacy Manual.

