#### **10.4 Prior and Concomitant Medications**

All prescription and over-the-counter medications and herbal and nutritional supplements taken during the Long-Term study will be recorded on the designated CRF. All prior medications taken within 14 days of initiation of this study are to be recorded on the CRF which is also recorded in the appropriate CRF pages of Study SMA-001 as concomitant medication.

The Investigator may prescribe additional medications during the study, if the prescribed medication is not prohibited by the protocol. In the event of an emergency, any needed medications may be prescribed without prior approval, but the medical monitor must be notified of the use of any contraindicated medications immediately thereafter. Any concomitant medications added or discontinued during the study should be recorded on the CRF.

Medications that are contraindicated when combined with amifampridine phosphate are:

- Medicinal products with narrow therapeutic window
- Sultopride

Amifampridine phosphate should be used with caution when combined with the following products:

- Medicinal products known to lower the epileptic threshold
- Medicinal products with atropinic effects
- Medicinal products with cholinergic effects
- Non depolarizing muscle relaxant acting medicinal products

	SMA-002	Page 26
---	---------	---------

- Depolarizing muscle relaxant acting medicinal products.

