### 15.4 Secondary Endpoint

The secondary endpoint of the study is the QoL scores at Months 3, 6, 9, 12, 15, 21 and 27.

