### **15.6 Determination of Sample Size**

The study is not powered with respect to any endpoint and no hypothesis is being tested.

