n	xx
Mean (SD)	xx.x (xx.xx)
Median	xx.x
Min, Max	xx, xx
Was the patient previously treated for SMA other than amifampridine phosphate?	
No	n (%) xx (xx.x)
Yes	n (%) xx (xx.x)
Unknown	n (%) xx (xx.x)
SMN gene analysis result	
Negative	n (%) xx (xx.x)
Positive (mutated)	n (%) xx (xx.x)
Not examined	n (%) xx (xx.x)
Unknown	n (%) xx (xx.x)

Percentages are calculated on the number of patients (N) in the SAF analysis set.

* Time from onset of SMA symptoms was calculated as the difference in years from the year of the date of the informed consent and the year of onset of SMA symptoms reported in CRF.

Source: xxx.sas, Run on ddmmmyyyy

Reference Listings: [16.2.4.2.1](#)

Table 14.1.9. Medical History / SAF

Body System	Statistic	Amifampridine (N=xx)
Cardiovascular	n (%)	xx (xx.x)
Respiratory	n (%)	xx (xx.x)
Muscle-Skeletal	n (%)	xx (xx.x)
Ears, nose, eyes and throat	n (%)	xx (xx.x)
Hepatobiliary	n (%)	xx (xx.x)
Endocrine & Metabolic	n (%)	xx (xx.x)
Haemopoietic	n (%)	xx (xx.x)
Central nervous	n (%)	xx (xx.x)
Dermatologic	n (%)	xx (xx.x)
Genitourinary	n (%)	xx (xx.x)
Gastrointestinal	n (%)	xx (xx.x)
Psychiatric Diseases	n (%)	xx (xx.x)
Allergies	n (%)	xx (xx.x)

The counts are the number of patients with at least one "Yes" response for the body system.

Source: xxx.sas, Run on ddmmmyyyy

Reference Listings: [16.2.4.2.2](#)

Programming Note: "Other Body System" is also recorded, but is not included in the above table; it is listed only.

Table 14.1.10. Previous Diseases from Medical History by SOC and PT / SAF

System Organ Class Preferred Term	Statistic	Amifampridine (N=xx)
No. of patients with at least one previous disease	n (%)	xx (xx.x%)
System Organ Class 1	n (%)	xx (xx.x%)
Preferred Term 1	n (%)	xx (xx.x%)
Preferred Term 2	n (%)	xx (xx.x%)
Preferred Term x	n (%)	xx (xx.x%)
System Organ Class 2	n (%)	xx (xx.x%)
Preferred Term 1	n (%)	xx (xx.x%)
Preferred Term 2	n (%)	xx (xx.x%)
Preferred Term x	n (%)	xx (xx.x%)
System Organ Class x	n (%)	xx (xx.x%)
Preferred Term 1	n (%)	xx (xx.x%)
Preferred Term 2	n (%)	xx (xx.x%)
Preferred Term x	n (%)	xx (xx.x%)

Previous diseases are those reported in the "Medical History" form of the eCRF with item "Present at study start?" flagged as "No".
Abnormalities were coded using the MedDRA dictionary version 23. Primary System Organ Class and Preferred Term are presented.
Patients are only counted once per SOC and PT.
Patients can have more than one previous disease.

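### QoL scores recorded after a patient starts another SMA treatment stay in the efficacy summaries with no flag and no separate summary

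*SAP*

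**What the plan says.** **Treatment rules.** Protocol 10.4 states: "The Investigator may prescribe additional medications during the study, if the prescribed medication is not prohibited by the protocol". Its contraindicated list has two entries, sultopride and products with a narrow therapeutic window. Protocol 10.2.2 item 8 excludes "Treatment with an investigational drug (other than amifampridine) or device while participating in this study". The same section carries over the SMA-001 exclusion criteria as conditions of eligibility, without reproducing them. Protocol 10.1 lets earlier concomitant medication continue.

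**QoL analysis.** Protocol 9.2 makes the clinical efficacy of amifampridine, judged by QoL change, the secondary objective. Protocol 15.4 adds: "The secondary endpoint of the study is the QoL scores at Months 3, 6, 9, 12, 15, 21 and 27". SAP 10.1 puts into the efficacy set every patient with one dose and one QoL assessment after treatment began. SAP 10.11 says: "The efficacy analysis will be descriptive and will be presented on observed data only". The shells of Tables 14.6.1 and 14.6.2 show each scheduled visit plus EOS. SAP 10.7 keeps unscheduled measurements out of by-visit summaries.

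**Other SMA treatment.** The shell of Table 14.1.8 asks: "Was the patient previously treated for SMA other than amifampridine phosphate". That is a history item. During the study, SAP 10.10.3 limits concomitant medications to a listing (16.2.8), and SAP 10.4 plans no subgroups. Under SAP 10.13 even use of a prohibited medication is only counted as a major deviation, with no stated effect on the efficacy set.

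**The concern.** The SAP treats earlier SMA treatment as worth describing at baseline but does not connect SMA treatment started later to the QoL results. Follow-up runs to Month 27 in a small single-arm study whose patients are divided between INQoL and PedsQL if adults and children both enrol. In groups that small, a few patients who start something else can move a mean visibly, and the reader of the tables and the mean-and-SD plots would not know.

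The movement could go either way. SAP 10.2 takes the QoL baseline for most patients from Day 0 of SMA-001, which the protocol synopsis describes as the end of the Run-in, so after dose titration. The synopsis also says that the study looks for lack of tolerance to the QoL effect. For a question about maintained benefit, the likelier harm is that another treatment hides a loss of effect.

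One INQoL endpoint is exposed by its wording. The perceived treatment effects score rests on items about any treatment for the muscle condition, so it cannot by itself separate amifampridine from an added therapy.

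**Working it through.** **No planned figure to reproduce.** The synopsis says "About 12 SMA Type 3 ambulatory patients will be studied", without derivation, and Protocol 15.6 says "The study is not powered with respect to any endpoint and no hypothesis is being tested". Protocol 10.3.4 confirms that there is no comparator: "All patients will receive open label amifampridine". The check is therefore a reading of the rules, followed by simple arithmetic.

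**Step 1: can a patient start another SMA treatment?** The general permission in Protocol 10.4 covers any medication that is not prohibited. The bars that apply after entry are investigational drugs and devices, sultopride and narrow-therapeutic-window products. A non-investigational SMA treatment outside those classes is not barred. This is inference: no section names such treatment as allowed.

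**Step 2: what happens to the later scores?** SAP 10.1 does not remove the patient, SAP 10.11 does not remove or separate the scores, and no listing or table marks them. Scheduled and EOS scores therefore stay in.

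**Step 3: how far could the mean move?** Let n be the patients with a QoL change at a visit on one instrument, k the number who have started another SMA treatment, and d the average change in points due to it.

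shift in mean change = k × d / n

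Per affected patient this is d/12 = 8.3% of d at n = 12, and d/6 = 16.7% of d at n = 6. The planned total of about 12 supplies n = 12. The value n = 6 assumes an even split between instruments. The documents give neither that split nor any value for k or d, so the values below are illustrative.

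| n | k | k/n | Shift at d = 10 | Shift at d = 20 |
|---|---|---|---|---|
| 12 | 1 | 8.3% | 0.8 | 1.7 |
| 12 | 2 | 16.7% | 1.7 | 3.3 |
| 12 | 3 | 25.0% | 2.5 | 5.0 |
| 6 | 1 | 16.7% | 1.7 | 3.3 |
| 6 | 2 | 33.3% | 3.3 | 6.7 |
| 6 | 3 | 50.0% | 5.0 | 10.0 |

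For example, 2 × 20 / 6 = 6.7 points. If d is a benefit, a true mean decline of 6.7 points would then show as no change.

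**The case against.** Several points stand against making more of this.

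- The phrase about observed data is a missing-data statement. SAP 10.12 uses it for safety and explains it as no imputation, and SAP 11.2 agrees. The gap is therefore silence about the event, not a decision to credit another therapy to amifampridine. Keeping every observed score is a legitimate treatment-policy summary. This stands, and the main summary should not change.
- The SMA-001 exclusions might have kept some SMA treatments out at entry. Their text is not available. As worded they govern eligibility rather than later starts, so they narrow the concern without closing it.
- The event can be traced by hand. Listing 16.2.8 gives start date, reason and indication, and the QoL listings give each patient by visit. That is feasible with about a dozen patients. However, nothing links the two, and a reader choosing after the fact which scores to discount would already know the scores.
- Dropping later scores has its own bias. Patients may add a treatment because they are worsening, so the remaining mean could look too good. This stands and must be stated beside the supplementary summary.
- The concomitant record covers medications and supplements. INQoL counts surgery and physiotherapy as treatment, so non-drug treatment is not reliably captured. This also stands.

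A reader might infer that a change caused by another therapy will be reported as amifampridine efficacy, or that one or two patients could account for the whole mean change. The documents support neither. They do not show that anyone started such a treatment, and they give no expected mean change or standard deviation to compare a shift with.

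**Conclusion.** The point holds conditionally. The SMA-002 text leaves room to start a non-investigational SMA treatment, and the SAP keeps the later scheduled and EOS scores without flag or separate summary. If that happens, the reported mean change moves by k × d / n, or 8.3% to 16.7% of d per affected patient for n between 12 and 6. The result rests on assumed k, d and n per instrument and on a permission inferred from general wording. The number of affected patients is unknown and may be zero.

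The analysis is descriptive and secondary, and the primary safety objective is untouched. Disease course and open-label expectation enter the same means, so handling this event would not make the remaining change attributable to amifampridine. It would expose one identifiable confounder. This is a cheap improvement, not a defect that invalidates the analysis.

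**What to change.** Keep the main all-observed summary as it is. Before database lock, add to SAP 10.11 wording such as:

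> Medications in Listing 16.2.8 that have SMA as the indication and were newly started during SMA-002 will be identified at data review without reference to QoL scores. The number of affected patients will be reported. Their visits after the first such start will be flagged in Listing 16.2.6.1. Tables 14.6.1 and 14.6.2 will be repeated as a supplementary summary using only assessments before the first such start.

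The cost is one review of the medication listing, one flag and one extra run of two tables. It needs no new data and changes no treatment rule. If nobody is affected, a sentence saying so replaces the extra tables.

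State the limits with the output:

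- There will be fewer observations at late visits.
- Censoring may be informative, so the two summaries must be read together.
- Non-drug treatments are not reliably captured.
- The remaining change is still uncontrolled.
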